2 STUDY RATIONALE

In a previous study, [name] team has shown that treatment of 128 patients with NorFlo[®] (curcumin-phospholipids (Meriva[®] 600mg) 2 tablets/day) in combination with conventional therapy was capable of reducing the 88% of relapses in patients with recurrent anterior uveitis (RAU) (**Figure 8**). The enrolled subjects suffered from uveitis of different etiologies. The three main different etiological groups of enrolled subjects were herpetic uveitis, autoimmune inflammatory ocular disease and various origin anterior uveitis. A few months after starting the treatment, a significant improvement in symptoms associated with relapse, like the ciliary pain, blurred vision, hyperemia and the presence of aqueous humor cells was observed in 42% of the treated patients. Only 8% of the patients worsened and required other treatments, such as sub-Tenon space injections. Among the three groups of RAU etiology, the patients that were most sensitive to the treatment with NorFlo[®] belonged to the autoimmune RAU etiology (n=56) ²⁶.

Figure 8 - A) Total number of patients with relapses before (blue) and after (red) Norflo therapy. B) Total relapse number before (blue) and after (red) Norflo therapy.

Relapse of uveitis is defined as an occurrence of anterior chamber cells of grade 1+ or higher according to the Studies of Uveitis Nomenclature criteria. In cases in which view of the anterior chamber is impaired by the loss of corneal clarity, a relapse will be defined as new corneal findings of endothelial inflammatory deposits or edema obscuring the anterior chamber in the absence of other causes of corneal edema and combined with two or more of the following features: conjunctival hyperemia, photophobia, decreased vision, or pain.

These extraordinary results provide the rationale to further study the effectiveness of curcumin-phospholipids in autoimmune HLA-B27-associated uveitis, which represents the most common type of uveitis (75% of total uveitis). NORFLO[®] ORO will provide a synergistic anti-inflammatory effect and will counteract the occurrence of cystoid macular edema, which is the most serious complications associated with the HLA-B27-associated uveitis. We expect that treatment with NORFLO[®] ORO will reduce recurrence of anterior uveitis in patients with HLA-B27-associated uveitis by targeting trigger factors such as inflammation, and the side effects related to the pathology (cystoid macular edema, synechia, keratophathy) overall improving the quality of life of the treated patients.

The study will be conducted by inserting a group of control patients and diagnostic ophthalmologic analysis, including analysis with the Kowa Laser Flare Meter instrument (LFM).

The role of intraocular inflammation in the disruption of the blood-aqueous barrier leading to the spreading of proteins and inflammatory cells into the aqueous humor has been well documented. To evaluate and grade this kind of inflammatory leakage (flare) in the anterior chamber (AC) of the eye the Standardization of Uveitis Nomenclature (SUN) is generally used. Grading, which ranges between 0 and 4+, is unreliable and not useful to detect and give a correct measurement of AC inflammation because it relies on the subjectivity of evaluation and the nonlinear grading of flare at the slit-lamp, therefore subjected to high variability.

Currently, the only system that allows to quantitatively, reproducibly and objectively measure intra-ocular inflammation is the Kowa Laser Flare Meter (LFM) instrument. Such instrument includes a photomultiplier that amplifies the intensity of the light scattered by

small molecules (flare) or larger particles (inflammatory cells) in the aqueous humor. The information is then processed by a computer and the result is expressed in photon counts per millisecond (ph/ms).

LFM instruments can quantify back-scattered light both from small molecules and from larger particles such as inflammatory cells.

LFM measurements may be unreliable in eyes with extensive posterior synechiae or mature cataract due to increased background scattering of light. Seven measurements are usually obtained, the highest and lowest values are discarded and the mean and standard deviation of the remaining five readings are automatically calculated. Patients do not experience any pain or discomfort during measurements. Aqueous flare intensity has been found in the range of 2.9–3.9 ph/ms in healthy individuals between 20 and 40 years of age. Flare values have been found to increase slightly with age, reaching 5.0–6.5 ph/ms in subjects between 70 and 80 years of age. Flare values < 10 ph/ms are considered normal.

Effective management of uveitis requires a reproducible and quantitative method to determine and monitor intraocular inflammation. It has become evident that clinically meaningful changes in flare counts could be achieved both in low and high-flare situations because LFM allows measuring flares ranging between 3 and 1000 ph/ms on a linear scale. Gonzales *et al.* reported an inverse relationship between LFM flare and visual acuity in patients with uveitis. While no relationship was found between complications and anterior chamber cell or flare scores at the slit-lamp, a strong relationship was found between LFM flare and visual between LFM flare and complications such as posterior synechia and macular edema, highlighting the importance of utilized LFM as diagnostic tool.

HLA-B27-Associated Acute Anterior Uveitis

The inflammatory pattern of acute HLA-B27-associated anterior uveitis has been evaluated using LFM. In a study on 44 patients presenting an acute episode of anterior uveitis, the mean initial flare was 160 ± 22 ph/ms (range: 11–787 ph/ms). All patients were given standard therapy consisting of hourly instillations of 1% prednisolone drops progressively tapered after 3 days according to the evolution of inflammation. A 50% and 90% flare reduction occurred after 2 and 8 days, respectively, under the standard therapeutic regimen used. In 15 out of the 44 patients enrolled, an additional periocular corticosteroid injection was needed because of insufficient flare decrease (less than 30% of initial flare) or because of flare reduction occurred between 10h and 24h. The end of an episode of anterior uveitis was defined as a flare level below 8 ph/ms. This study demonstrates that LFM allows meticulous adjustment of therapy in patients with HLA-B27-associated uveitis.

The sensitivity of LFM in monitoring anterior chamber inflammation in HLA-B27associated uveitis has been further evaluated in a recent study that compared LFM measured values to slit-lamp grading system of aqueous cells. In this prospective masked trial, the mean time for a 50% reduction was 3.9 days for LFM flare and 14 days for aqueous cells. The mean time for a 90% reduction was 19.6 days for LFM flare and 40 days for aqueous cells. Based on these results, the authors concluded that LFM flare was a more sensitive parameter than the slit-lamp grading of cells in assessing evolution of acute anterior uveitis. Currently, uveitis specialists who use LFM as diagnostic instrument continue treatment until LFM flare returns to normal levels following an episode of HLA-B27-associated acute anterior uveitis **29-35**.

3 STUDY OBJECTIVES

3.1 **Primary Objective**

To explore the efficacy of NORFLO[®] ORO in RAU, measured as a long-term reduction of the frequency and severity of relapses, in patients with HLA-B27-associated uveitis, under conditions of routine medical practice. The reduction of the mean number of relapses per patient between the year before study treatment and the study period will also be assessed.

3.2 Secondary Objectives

The secondary objectives of this study include:

- the evaluation of the improvement of side effects due to HLA-B27-associated uveitis such as IOP, cystoid macular edema, keratopathy and synechia;
- the evaluation of the improvement in uveitis-related symptoms (BCVA and symptoms measured by VAS like ocular pain, photophobia, floaters and blurred vision).
- the evaluation of cell damage and inflammation reduction in patients with HLA-B27associated uveitis;
- the evaluation of the patients' attitude towards the study treatment;
- the evaluation of the safety profile of the study product.

4 STUDY DESIGN

4.1 **Study Overview**

This is a multicenter, double blind, placebo-controlled and randomized study. This study will be conducted in compliance with both European and FDA requirements.

Patients eligible for participation in this study, as part of their routine medical care, will receive NORFLO[®] ORO or placebo in addition of the conventional therapy. In the study, patients will be followed up to 1 year. This study will include patients with HLA-B27-associated relapsing uveitis. Participating sites will be encouraged to enroll patients in both

cohorts (NORFLO[®] ORO or placebo), through an e-based randomization system in order to minimize bias in patients' selection.

Sixty subjects with HLA-B27-associated uveitis will be enrolled and they will be divided into 2 groups, 30 will receive the treatment and 30 the placebo, in addition to conventional therapy. In Italy 46 patients will be recruited.

Each subject will receive a single dose of either placebo or NORFLO[®] ORO two times a day for 1 year. Subjects will be assigned to the treatments in a random order. Evaluations will be taken at baseline (t₀) and during each of the following two visits within the study (t1 6 months, t₂ 12 months).

Data from screened patients will be reviewed to determine the subject eligibility. Subjects who meet all inclusion criteria and none of the exclusion criteria will be enrolled in the study and randomized to treatment.

The following treatment regimens will be applied:

- NORFLO[®] ORO 1.7450 gr
- Placebo 1.7450 gr

Total duration of subject participation will be of about 12 months. Total duration of the study is expected to be about 15 months.

	Dosage regimen/Each center	Administration	Duration
NORFLO [®] ORO	3.49 gr total (2 single foil pouches of 1,7450 g) per day	Each single pouch (1,7450 g) at main meal in a glass of water	12 months
PLACEBO	3.49 gr total (2 single foil pouches of 1,7450 mg) per day	Each single pouch (1,7450 g) at main meal in a glass of water	12 months

Table 1 – Dosage Regimen

5 CRITERIA FOR EVALUATION

5.1 **Primary Efficacy Endpoint**

The primary efficacy endpoint will be the mean number and intensity of relapses per patient occurred during the study, from baseline to end of treatment, in patients treated with the NORFLO[®] ORO compared to patients treated with placebo.

The reduction in relapses will be determined by a reduction of the intraocular inflammation through a clinical and diagnostic evaluation that includes Laser measurement of AC flare

with Kowa LFM 600 or LFM 700 (Normal range 2.5-7 ph/ms. Outside normal range > 10 ph/ms).

The reduction of the mean number of relapses per patient between the year before treatment and the study period within each treatment group will also be assessed.

The reduction of cell damage and inflammation will be measured by the Laser Flare Meter, in patients affected by HLA-B27-associated uveitis after treatment with NORFLO[®] ORO, when compared to placebo.

5.2 Secondary Efficacy Endpoints

The following secondary endpoints will be examined:

- The reduction of the side effects due to HLA-B27-associated uveitis, such as IOP assessed by Goldmann applanation tonometry (APL), cystoid macular edema (central foveal thickness central 1 mm subfield thickness), assessed by optical coherence tomography (OCT) Spectralis[®] spectralis, keratopathy, evaluated by fluorescein staining of the cornea (present/absent), and synechiae, assessed by photographic slit lamp (present/absent and if present, involving one or more quadrants; photographs shall be retained to document synechia), after treatment with NORFLO[®] ORO, when compared to placebo.
- The improvement in uveitis-related symptoms (BCVA, symptoms like ocular pain, photophobia, floaters and blurred vision, measured by VAS) after treatment with NORFLO[®] ORO, when compared to placebo.
- The patients' attitude towards the treatment with NORFLO[®] ORO, compared to placebo, will be captured by means of a questionnaire (Quick Questionnaire) specifically developed for the study on the basis of previous experiences^{4,36-39}.

5.3 Safety Evaluations

The safety evaluations will include:

- The incidence and typology of adverse events in the NORFLO[®] ORO treatment group compared to placebo group.
- The use of concomitant medications.
- The changes in vital signs.

6 SUBJECT SELECTION

6.1 Study Population

Subjects with a diagnosis of HLA-B27-associated uveitis who meet the inclusion and exclusion criteria will be eligible for participation in this study.

6.2 Inclusion Criteria

- 1. Subjects \geq 18 years of age at baseline Visit.
- 2. HLA-B27 positive related uveitis (acute alternating non granulomatous uveitis the uveitis shall not be in acute phase at the time of enrolment and at least 8 weeks must have elapsed after the resolution of the last uveitis attack.
- 3. Subjects with at least one autoimmune uveitis relapse (UAR) in the last year.
- 4. Written informed consent obtained from subject or subject's legal representative and ability for the subject to comply with the requirements of the study.

6.3 Exclusion Criteria

- 1. Presence of a condition or abnormality that in the opinion of the investigator would compromise the safety of the patient or the quality of the data collected.
- 2. Subjects that have received systemic therapy for uveitis with anti-inflammatory, immunosuppressive or biological drugs in the 30 days before study start.
- 3. Subjects with an anticipated need for systemic anti-inflammatory, immunosuppressive or biological drugs during the 12 months of the study.
- 4. Subjects who received an intravitreal, peribulbar, sub-tenon, periocular injection in the previous 6 months.
- 5. Subjects that are receiving long-term treatment with systemic anti-inflammatory, immunosuppressive or biological drugs for other diseases different from uveitis.
- 6. Women who are taking hormonal contraceptives.
- 7. Subjects that have taken supplements and nutraceuticals in the last 30 days prior to baseline visit. Use of supplements and nutraceuticals will not be admitted during the study.
- 8. Subjects for whom baseline LFM and other ocular evaluations cannot be accurately performed.
- 9. Women who are pregnant or breast-feeding.

The study will be considered completed once the last clinical site will be closed. Participation in this study has no impact on the type of medical care that the patient will receive during the study as well as post-study participation.

7 CONCURRENT MEDICATIONS

All subjects should be maintained on the same medications throughout the entire study period, as medically feasible, with no introduction of new chronic therapies.

7.1 Allowed Medications and Treatments

All topical drugs (any topical midriatic treatment and any traditional topical therapy for uveitis) will be admitted for the treatment of the signs and symptoms associated with HLA-B27-associated chronic relapsing uveitis.

In the case of relapse with LFM values are > 100 ph/ms despite treatment with topical therapy, or in any case the LFM values result to be > 100 ph/ms, then a systemic therapy is recommended and the subject has to be dropped-out from the study and treated according to the best medical judgement.

7.2 **Prohibited Medications and Treatments**

The following medications are prohibited during the study and the administration will be considered a protocol violation: supplements and nutraceuticals, systemic therapies for uveitis (anti-inflammatory, immunosuppressive, biologicals), hormonal contraceptives, long-term treatment with systemic anti-inflammatory, immunosuppressive or biological drugs for other diseases different from uveitis. Systemic therapies with anti-inflammatory, immunosuppressive drugs are allowed for reasons different from uveitis and in any case for periods not exceeding 15-30 days.

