10.4 Additional Unscheduled Visits in Case of Relapse

Should a relapse occur, an unscheduled visit will be performed including a complete ophthalmic evaluation. The number of cells in the AC will be determined by slit lamp, too.

Topical or systemic treatment will be prescribed to the subject according to the severity of the relapse and according to the best medical judgement.

Two following visits will be scheduled 2 and 6 weeks thereafter. During these visits a complete ophthalmic evaluation will be done.

If the subject is prescribed a systemic treatment for the relapse, he/she will be withdrawn from the study, and treated according to the best medical judgement.

If only topical treatments are prescribed, the subject will be allowed to continue the study. Depending on the onset time of the relapse it could be necessary to delay Visit 2 or Visit 3 around 2 months after the topical treatment conclusion.

Should Visit 2 be delayed, the delay will be recovered by keeping the date of Visit 3 at 12 months.

Should Visit 3 be delayed, the delay will not be recovered.

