11 DISCONTINUATION AND REPLACEMENT OF SUBJECTS

11.1 Early Discontinuation of Study Drug

A subject may be discontinued from the study treatment at any time if either the subject, and/or the investigator, and/or Eye Pharma feels that it is not in the subject's best interest to continue the study treatment. The following is a list of possible reasons for study treatment discontinuation:

- Subject withdrawal of consent
- Subject is not compliant with study procedures
- Need for the subject to start a systemic anti-inflammatory, immunosuppressive, biologicals therapy for uveitis or for other pathologies
- Adverse event that indicated in the opinion of the investigator that it would be in the best interest of the subject to discontinue study treatment
- Pregnancy
- Protocol violation requiring discontinuation of study treatment
- Missed follow-up
- Eye Pharma requests early study termination

If a subject is withdrawn from treatment due to an adverse event, the subject will be followed and treated by the investigator until the abnormal parameter or symptom has resolved or stabilized.

All subjects who discontinue the study treatment should come in for an early discontinuation visit as soon as possible and then they should be encouraged to complete all remaining scheduled visits and procedures.

All subjects are free to withdraw from participation at any time, for any reason, specified or unspecified, and without prejudice.

Reasonable attempts will be made by the investigator to obtain a reason for subject's withdrawals. The reason for the subject's withdrawal from the study will be specified in the subject's source documents.

11.2 **Replacement of Subjects**

Only subjects dropping out the study because they are beginning systemic therapy with antiinflammatory, immunosuppressive, biologic drugs will be replaced.

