## 8. ANALYSIS POPULATIONS

# 8.1 Intent-to-Treat Population (ITT)

All eligible patients who are randomized into the study, receive at least one dose of the study product and have at \_\_\_\_ least a post-randomization endpoint estimate will be included in the efficacy analysis. Primary endpoints will be also analyzed in a modified Intention-to-Treat Population, where the patients with the protocol violations mentioned in the session 10.2 (Protocol Deviations) will be excluded.

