### 10.2 Protocol Deviations

A protocol violation occurs when either the subject, and/or the investigator, and/or Eye Pharma fails to adhere to significant protocol requirements affecting the inclusion, exclusion, subject safety, and primary endpoint criteria. Protocol violations for this study include, but are not limited to, the following:

- Failure to meet inclusion/exclusion criteria
- Compliance with study product regimen under 90%.

Failure to comply with Good Clinical Practice (GCP) guidelines is also a protocol violation.

Protocol deviations are minor deviations from the protocol (e.g., missing a visit window because the subject is traveling). Protocol deviations and violations will be summarized, separately for each treatment group and each study phase.

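### Protocol 7.2 classes systemic therapy for uveitis as a protocol violation, while 7.1, 10.4 and 11.1 handle it after a severe relapse as a planned withdrawal; the SAP leaves open whether such patients stay in the modified ITT.

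*Protocol*

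**What the plan says.** **The violation rule.** Protocol 7.2 states: "The following medications are prohibited during the study and the administration will be considered a protocol violation". Its list includes "systemic therapies for uveitis (anti-inflammatory, immunosuppressive, biologicals"). The only allowance in that section is for short systemic courses given for reasons other than uveitis.

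**The relapse rules.** Protocol 7.1, immediately before it, covers flare above 100 ph/ms: "then a systemic therapy is recommended and the subject has to be dropped-out from the study". Protocol 10.4, on the unscheduled relapse visit, says: "Topical or systemic treatment will be prescribed to the subject according to the severity of the relapse". It continues: "If the subject is prescribed a systemic treatment for the relapse, he/she will be withdrawn from the study". Protocol 11.1 gives as a reason for discontinuation: "Need for the subject to start a systemic anti-inflammatory, immunosuppressive, biologicals therapy for uveitis or for other pathologies". Protocol violation requiring discontinuation is a separate entry in the same list, and SAP 9.1.4 repeats both entries. Protocol 11.2 replaces only the subjects who leave to begin systemic therapy.

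**The analysis rules.** SAP 8.1 and 11.1 add a modified ITT for the primary endpoints, "where the patients with the protocol violations mentioned in the session 10.2 (Protocol Deviations) will be excluded". SAP 10.2 introduces its list with "Protocol violations for this study include, but are not limited to, the following". It names failed inclusion or exclusion criteria and product compliance under 90%, then adds GCP failure. Prohibited medication is not named. SAP 10.2 also has deviations and violations summarised by treatment group.

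**The concern.** A patient with a severe relapse who is given systemic therapy and withdrawn, as 7.1 and 10.4 provide, has followed the protocol and has broken it under 7.2. Two outputs inherit the ambiguity.

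The first is the by-arm violation summary. Read with 7.2, it would show treatment failure as poor conduct, and more of it in whichever arm has more severe relapses.

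The second is the modified ITT. No per-protocol analysis is planned (SAP 8.2), so this is the only alternative population for the primary endpoints. If violations under 7.2 count, patients leave it because of a primary-endpoint event. Protocol 14.3 scores a relapse severe at flare of 100 or more, and 7.1 points to systemic therapy above 100. The patients lost would therefore be largely those whose relapses are severe by flare, in an endpoint that covers both number and intensity. The decision would rest on judgement about an open list.

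**Working it through.** **1. The passages side by side.**

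| Section | Status of systemic therapy for a uveitis relapse |
|---|---|
| Protocol 7.1 | Recommended above 100 ph/ms; subject leaves the study |
| Protocol 7.2 | Prohibited; giving it is a violation; no exception |
| Protocol 10.4 | One of two routes, by severity and medical judgement; withdrawal follows |
| Protocol 11.1, SAP 9.1.4 | Own discontinuation reason, apart from protocol violation |
| Protocol 11.2 | Subject is replaced |
| SAP 11.4.1 | First unscheduled-visit data are used because they precede systemic and topical cortisone |

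Only 7.2 uses the violation label. SAP 11.4.1 expects relapses that go on to systemic therapy to supply primary-endpoint data.

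**2. From 7.2 to the modified ITT.** There are two routes, and neither is certain.

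- *Open list.* SAP 10.2 defines violations as failures on significant requirements, including those affecting primary endpoint criteria, and its list is not closed. Something the protocol itself calls a violation can be read in.
- *Compliance.* SAP 11.3 divides administered doses by planned doses, without defining planned doses for a withdrawn subject. If they cover the full 12 months, a fully adherent subject withdrawn at month 6 scores 6/12 = 50%. Anyone withdrawn before month 0.90 × 12 = 10.8 is under 90%, which SAP 10.2 does name. If planned doses stop at withdrawal, the score is 100% and this route closes.

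**3. How many patients could be involved.** The documents do not give the share p of relapses treated systemically, so p is an assumption. The other inputs are the design means of 2.6 (placebo) and 2.0 (active) relapses per patient and 30 patients per arm, from Protocol 14.7 and 4.1. With Poisson counts, the chance of at least one systemically treated relapse in 12 months is 1 − exp(−mean × p).

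| p | Placebo | Active | Of 30 placebo / 30 active |
|---|---|---|---|
| 5% | 1 − exp(−0.13) = 12% | 1 − exp(−0.10) = 10% | 3.7 / 2.9 |
| 10% | 1 − exp(−0.26) = 23% | 1 − exp(−0.20) = 18% | 6.9 / 5.4 |
| 20% | 1 − exp(−0.52) = 41% | 1 − exp(−0.40) = 33% | 12.2 / 9.9 |
| 30% | 1 − exp(−0.78) = 54% | 1 − exp(−0.60) = 45% | 16.2 / 13.5 |

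This ignores dropout for other reasons and replacement of subjects. The shares are not very sensitive to the Poisson shape: treating the count as fixed at its mean gives 1 − (1 − p)^mean, which at p = 10% is 1 − 0.9^2.6 = 24% and 1 − 0.9^2 = 19%.

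**4. Whether the route is rare.** Protocol section 2 cites a study of 44 patients with a mean initial flare of 160 ph/ms in acute HLA-B27 uveitis, above the 100 ph/ms threshold. The share of episodes above 100 cannot be read from a mean, but the figure gives no reason to think p is negligible.

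**The case against.** **Exclusion is inferred, not specified.** SAP 8.1 and 11.1 remove only violations mentioned in SAP 10.2, and prohibited medication is not among those named. This stands. A reader might infer that the SAP does remove these patients; the documents support only that it could.

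**The modified ITT is supplementary.** Primary endpoints are also analysed there, while the SAP 11.5 table gives ITT alone for them. This stands. The ITT keeps these patients if they have a post-randomisation estimate, whatever 7.2 calls them.

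**Section 7.2 applies during the study, and these subjects leave it.** This is a partial defence. The prescription is made at an on-study visit, and 11.1 encourages patients who stop study treatment to complete their remaining visits.

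**The protocol does not direct systemic therapy.** Correct: 7.1 recommends it and 10.4 leaves it to judgement. The mandatory part is the withdrawal.

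**A loss of power.** A reader might infer that the violation label costs the trial power. The calculation does not support that. At 30 per arm, difference 0.6 and SD 0.7, t-test power is 90%. (The same inputs at 80% power give 23 per arm, the plan's 46.) Dropping the affected patients leaves an expected difference of 0.6 × (1 − p) = 0.54, 0.48 and 0.42 at p = 10, 20 and 30%, with power 74, 54 and 35%. Now keep every patient but stop counting at the withdrawal that 7.1 and 10.4 require. The mean count becomes (1 − exp(−mean × p))/p, the differences are 0.48, 0.38 and 0.30, and power is 74, 54 and 37%. The loss comes from the withdrawal, not the label. The setting is also inconsistent: Poisson counts at these means have SDs of √2.6 = 1.61 and √2.0 = 1.41, not 0.7, and at those SDs power is about 33% before anyone is excluded.

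**Conclusion.** The contradiction is established from the text alone: 7.2 calls a violation what 7.1, 10.4 and 11.1 handle as a planned withdrawal. Following 7.2 literally would put protocol-managed severe relapses into the by-arm violation summary. Their removal from the modified ITT is a possibility that the SAP leaves open, and it would be an outcome-dependent exclusion.

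On the Poisson assumption, the share open to exclusion runs from 12% placebo and 10% active at p = 5% to 54% and 45% at p = 30%. The imbalance between arms is about 3 to 9 percentage points if the design effect is true. These are ceilings that apply only if the open list or the compliance denominator is read that way. The main ITT analysis is untouched by the label, and no claim about power follows. The point is worth settling before unblinding because it bears on the only alternative population for the primary endpoints and costs little to close.

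**What to change.** 1. **Protocol 7.2.** Reconcile it with 7.1, 10.4 and 11.1, so that systemic therapy prescribed for a relapse under those sections is recorded as relapse-related withdrawal and not as a protocol violation. This concerns classification only; when systemic therapy is given does not change.
2. **SAP 8.1 and 10.2 (and the matching text in 11.1).** Replace the open list, for the purpose of the modified ITT, with a closed list of the violations that exclude a patient. State that systemic therapy for a relapse, or the withdrawal that follows it, is not one of them, and that these patients stay in with their relapses counted. Making the second part work also requires SAP 11.3 to say what planned doses means for a withdrawn subject.

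The cost is a few sentences in the two documents and no new data. The downside is that the modified ITT moves closer to the ITT and so offers less of a contrast with it.
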